The purpose of the present funding opportunity (PAR-17-156) is to begin to evaluate, with a high degree of fidelity, ECs as a potential means of reducing smoking-related risks and to provide information on the use and effects of JUUL; it is also meant to be completed quickly (two-year study). In order to successfully execute our research plan, we will conduct the present study with a quitline (QL) population, characterized by high levels of nicotine dependence, low socioeconomic and educational attainment, and high levels of substance use and mental health disorders—priority populations for tobacco control. QLs provide ready access to a large number of tobacco users, as well as infrastructure for delivering and testing study interventions. Our team has successfully carried out large-scale QL recruitment (e.g., 2,000 smokers in 8 months) for past trials. QLs are potentially the best real-world platform to quickly and with sufficient statistical power, meaningfully examine smokers' willingness to switch to JUUL and its downstream effects on smoking and health.

Therefore, the overall aim of the proposed study is to evaluate the provision of JUUL versus NRT on smoking behavior, product use patterns and continued use, and iCO, a biomarker of toxicant exposure, among a sample of recent QL treatment failures. We will randomly assign 420 smokers to JUUL or treatment as usual, combination nicotine replacement therapy control (NRT). All participants will receive three calls from QL coaches and JUUL and NRT will be provided at no cost for 8 weeks. The final follow-up will occur 12-weeks post baseline.

Aim 1: To assess JUUL vs. NRT on product switching/substitution, craving/withdrawal, abuse liability, number of cigarettes smoked, and perceived nicotine dependence. *Hyp 1a: Complete product substitution (vs. partial or no substitution) will occur at a significantly higher rate among smokers randomized to the JUUL compared to those randomized to NRT at 8 and 12-week follow-ups. Hyp 1b: Compared to those randomized to NRT, JUUL participants will report less nicotine craving, fewer nicotine withdrawal symptoms, smoke fewer cigarettes per day, and higher perceived nicotine dependence.*

Switching to a Vaping Device: Evaluating Risk Reduction among Quitline Treatment Failures

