Sociodemographic data will assess participant age, sex, marital status, ethnicity, employment status, occupation, years of education, and socioeconomic status. Tobacco use history will assess years of smoking, age of smoking onset, average number of cigarettes per day, number and recency of previous 24-hour quit attempts, number of smokers in the household, prior use of nicotine replacement therapy and other stop smoking medications, and history of receiving smoking cessation counseling, and cigarette and EC expectance effects. It will also assess tobacco type, brand, frequency, quantity, and duration of use all of nicotine/tobacco products including cigars, cigarillos, little cigars, pipe tobacco, chewing tobacco, snuff, snus, EC, combustible tobacco hookah, and dissolvable tobacco. Complete Substitution will be defined as ≥7 days with no more than 1 conventional cigarette smoked (assessed via EMAs), daily exhaled carbon monoxide of ≤6 ppm as measured by iCO (see biomarker measures below), and reported use of ECs over the same 7-day period.

Switching to a Vaping Device: Evaluating Risk Reduction among Quitline Treatment Failures

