All participants will be mailed a study smartphone and iCO device, and provided 3 months of unlimited call and data service at no charge and will complete EMAs twice a day for all 12 weeks. Participants will receive one EMA delivered randomly during the day and an evening daily diary (~30 minutes before bedtime). Given the half-life of CO (4-12 hours), we will only request that participants complete iCO measurement for the evening daily diary. Consistent with our team's previous studies, random EMAs will assess: mood, affect, nicotine craving and withdrawal symptoms, stress, recency of vaping/smoking, alcohol use, current setting, and switching self-efficacy; daily diary EMAs will assess conventional cigarettes smoked per day, number of JUUL pods used (if applicable), cigarette/EC satisfaction and pleasure, and measurement of exhaled carbon monoxide with the iCO (see Table 2 for specific EMA measures). All EMAs will be prompted and initiated by the phone. The phone will audibly and visually cue these EMAs for 30 seconds. If the participant has not responded after 3 prompts, the assessment will be recorded as missed. Typically, random sampling assessments take ~1-2 minutes to complete and daily diary assessments take approximately ~3-4 minutes to complete. Participants will be compensated for EMA completion at the 8 and 12 week follow-ups. All assessments will be date and time stamped for future analyses. Participants have the ability to call (e.g., if they have problems completing EMA's) and receive calls from research staff through the smartphone free of charge. The EMA methodology used in this study has been successfully followed by our team as well as other researchers in multiple studies.¹¹⁹⁻¹²⁸ All participants will be sent prepaid mailing boxes and asked to return

Switching to a Vaping Device: Evaluating Risk Reduction among Quitline Treatment Failures

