Aim 3: The focus of aim 3 is (Hyp 3a) to determine which EC device characteristics and perceived effects are associated with complete (vs. partial or no) substitution. *Hypothesis 3a:* We will examine whether changes in EC device characteristics and perceived effects obtained by EMA over time differ between those who achieve complete (vs. partial or no) substitution using linear mixed model (LMM) regression analysis. We will employ a random intercept or slope parameter, as appropriate, and model the covariance structure for the repeated outcome measures, while accounting for potential confounders. We will use similar methods to explore return to smoking in those who report complete substitution at any time during the study.

3. Missing Data

In the event of missing data, we will contact participants immediately. If a participant drops out, we will attempt to gather follow-up information by calling the study phone and trying to reach the participant through other provided contact information. However, if a participant refuses to be contacted or loses contact with the investigators, we will censor data at point of loss. Two statistical approaches will be used to handle missing data. First, we will use inverse probability weighting with propensity scores. This is a two-step procedure in which we first model the probability of missingness as a function of baseline covariates and previous outcomes. Next, the inverse of the resulting predicted probabilities (from the logistic regression model) will serve as weights in our proposed model of the response. We will compare these results to a more conservative ITT approach as a final step.

Switching to a Vaping Device: Evaluating Risk Reduction among Quitline Treatment Failures

F. Gender/Minority/Pediatric Inclusion for Research

1. Inclusion of Women and Minorities

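### Return to smoking after a switch is to be explored by analogy with a linear mixed model, with no event, time origin or censoring rule defined, although time at risk runs from about 77 days to almost none

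*Combined protocol and SAP*

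**What the plan says.** Section E.2 (Data Analytic Plan), Aim 3, Hypothesis 3a compares ratings of device characteristics and perceived effects, collected by EMA, between people with "complete (vs. partial or no) substitution using linear mixed model (LMM) regression analysis". On the model it says: "We will employ a random intercept or slope parameter, as appropriate, and model the covariance structure for the repeated outcome measures". The paragraph then closes with "We will use similar methods to explore return to smoking in those who report complete substitution at any time during the study". The linear mixed model is the only method named in that paragraph, so it is the natural meaning of similar methods.

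Four other provisions bear on the point:

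- Section D.3 (Measures): "Complete Substitution will be defined as ≥7 days with no more than 1 conventional cigarette smoked (assessed via EMAs". The definition also requires daily exhaled CO of 6 ppm or less and reported e-cigarette use over the same period.
- Section A (Specific Aims): "The final follow-up will occur 12-weeks post baseline".
- Section D.3, on EMA and iCO: participants "will complete EMAs twice a day for all 12 weeks". Cigarettes per day and CO are recorded in the evening diary.
- Section E.3 (Missing Data): for people lost to contact, "we will censor data at point of loss", with inverse probability weighting and an ITT comparison.

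The plan does not define return to smoking as an outcome, say when its clock starts, or name a survival method.

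**The concern.** A person can return to smoking only after having switched, and the switch can come on almost any day of the study. Everyone is then followed to the same study end. Someone who first meets the 7-day criterion in week 1 can be seen to relapse over eleven weeks; someone who meets it in week 11 has about one week. A tabulation or model that ignores this mixes two things: how likely a switcher is to go back to smoking, and how long that switcher was watched.

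Whether switching lasts is one of the questions the surveillance phase is there to answer. If late switchers fill the non-returner group because follow-up ran out, then any description of who returns, or of which ratings go with returning, partly describes when people switched.

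The weighting in Section E.3 does not deal with this. It models dropout. Late entry into the risk period with a common end date is not dropout.

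**Working it through.** The documents give no figure for return to smoking, so there is nothing of the plan's own to reproduce. The check asks how far unequal time at risk alone can move the result, and under which analysis.

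**Inputs from the documents.** Follow-up ends on day 84 (12 weeks). The criterion needs at least 7 days, so the earliest switch is about day 7. Attrition is 20% (Section E.1).

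**Assumptions, not in the documents.** Everyone has the same constant hazard of returning, set so that 20%, 50% or 80% would return over 84 days at risk.

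**Step 1: time at risk.** For a switch on day s it is 84 − s. Day 7 gives 84 − 7 = 77 days; day 77 gives 84 − 77 = 7 days.

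**Step 2: proportion returned by week 12.** With h = −ln(1 − p)/84, the expected proportion is 1 − exp(−h(84 − s)). For p = 0.50 and s = 28 this is 1 − 0.5^(56/84) = 0.370.

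| Return over 84 days (assumed) | Switch day 7 | Day 28 | Day 56 | Day 77 |
|---|---|---|---|---|
| 20% | 18.5% | 13.8% | 7.2% | 1.8% |
| 50% | 47.0% | 37.0% | 20.6% | 5.6% |
| 80% | 77.1% | 65.8% | 41.5% | 12.6% |

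The differences along each row come only from length of observation.

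**Step 3: what different analyses make of it.** The proportions above do not evaluate a mixed model, so models were fitted to a simulated data set. It had 3,000 switchers, all with the 50% hazard. About half switched early (days 7 to 35) and half late (days 50 to 77). The mixed models had a random intercept and used weekly status (returned by that week, yes or no). A correct analysis should show no early-versus-late difference.

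| Analysis | No dropout | 20% dropout |
|---|---|---|
| Ever returned, early vs late | 40.8% vs 14.1% | 36.8% vs 12.8% |
| Mixed model, no time term: early coefficient (SE) | 0.145 (0.012) | 0.135 (0.012) |
| Mixed model, study time | 0.274 (0.012) | 0.275 (0.012) |
| Mixed model, time since switch | 0.014 (0.012) | 0.018 (0.012) |
| Cox from switch date: HR (95% CI) | 1.14 (0.95 to 1.35) | 1.09 (0.91 to 1.31) |

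On study time, a given week compares early switchers who have been at risk for a long time with late ones who have just entered, hence a false difference of about 27 percentage points. On time since switch, or with a survival model from the switch date, the estimates are compatible with no difference.

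**The case against.** The strongest reply is that the plan never says return to smoking is a first-event outcome. In Hypothesis 3a the response is a repeated EMA rating and substitution status is the grouping variable. The closing sentence could mean the same structure, with rating trajectories compared between switchers who did and did not return. It could also mean daily cigarettes as the response, which Hypothesis 1b already models this way. A linear mixed model suits either response. It accommodates unequal follow-up and, if data are missing at random, uses everything up to the point of loss.

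This stands in part. A reader might infer that a mixed model cannot handle the question at all, or that early switchers are bound to look worse. The documents support neither reading: outcome coding and time axis are left open, and the model on time since switch showed essentially no distortion. But under the trajectory reading the grouping itself, returned or not by study end, is affected by unequal observation, however well the model handles the ratings. Under the cigarettes reading, the time axis still has to be chosen.

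It is also fair to say that event days will not all be known. Prompts left unanswered are recorded as missed, payment starts at 50% completion, and the team reports completion above 80% in previous studies. If each diary day were completed independently with probability 0.8, a 7-day window would be complete with probability 0.8^7 = 0.21. Missed days probably cluster, so this only illustrates the need for a rule.

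Finally, the analysis is described as exploratory, and the comparison of complete substitution at weeks 8 and 12 addresses persistence separately.

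**Conclusion.** The point holds in a limited form. The plan points return to smoking towards a linear mixed model without defining the outcome, the time origin or the censoring rule, in a subgroup whose time at risk varies from about 77 days to almost none. Coding by week 12, study time as the axis, or no time term can each produce a difference between early and late switchers where none exists. In the simulation this was 26.7 points on the crude proportion (40.8 − 14.1) and 0.145 to 0.274 in the mixed models without dropout. Those sizes rest on an assumed common hazard and on deliberately separated switch dates, so they show the mechanism and are not a forecast.

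A reader might go further and infer that JUUL would be penalised for producing earlier switching. The documents do not support that. The sentence states no contrast between arms, and because Complete Substitution requires e-cigarette use, few participants using only NRT would enter this subgroup on the literal definition.

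The primary outcome, the power calculation and the randomised comparisons are unaffected. The change is still worth making, because a clearly better method exists and needs no new data.

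**What to change.** Replace the closing sentence of Aim 3 with a time-to-event analysis of the daily diary and CO data:

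- **Time zero:** the day the 7-day Complete Substitution criterion is first met.
- **Event:** the first later day on which the rolling 7-day smoking criterion fails, meaning more than one cigarette in the window or a CO reading above 6 ppm. Stopping e-cigarette use without smoking should not count as a return.
- **Censoring:** at the last diary entry or week 12, whichever comes first.
- **Model:** discrete-time with complementary log-log link, or Cox, with product supply (before or after week 8) as a time-varying term. Early switchers contribute time on and off supply; those switching after week 8 contribute only time off supply.
- **Missed diary days:** a stated rule, and a sensitivity analysis that treats affected event days as interval-censored.
- **Interpretation:** any comparison of arms reported as associational, because the subgroup is formed after randomisation.

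If the team prefers a repeated measure such as cigarettes per day, the mixed model can stay, but the SAP should name that response and index it by time since switch.

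The cost is SAP wording and slightly more programming.

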TLFB		x	x	Cigarette/Vape Availability
Motivation Rulers – 8 to 12		x	x	Cessation Motivation
Cigarette Purchase Task		x	x	Smoking Restriction
iCO		x	x	Vaping Restriction
				Cigarette Reward Value
				Alcohol Use

* Daily Diary EMAs also include Random EMA items

E. Statistical Methods

1. Power Analysis

Complete substitution of combustible cigarettes for EC products is the primary outcome of the study, as the rate of product substitution will likely drive the outcomes for all of the other aims. We will compare the proportion of participants with complete substitution in the JUUL vs. NRT at the end of the product trial phase (8-week follow-up) using the Fisher's exact test. There are no direct data available on which we can base sample size estimates for the proposed study. The closest estimate for the JUUL arm was based on the 6 week, 35% switch rate for JUUL in a pilot study of a community sample of African American/Black smokers ([name], personal communication). Likewise, we estimate that the percent of complete substitution will be 35%. For the NRT, the closest estimate was the 4 week, 30% abstinence rate for preferred NRT product among a sample of smokers motivated to quit smoking¹⁵⁶; however, we will conservatively assume a NRT substitution rate of 20% since participants will have tried NRT previously and were not successful. We will assume an attrition rate of 20%. Assuming 20% attrition among a total of 420 participants (186/group), will allow 300 participants to be analyzed in the final sample. A sample size of 300 will provide >80% power to detect a difference in complete substitution between JUUL and NRT groups for a two-sided .05 level chi-squared test. It is important to note that this sample size is deliberately conservative, as it does not assume the availability of repeated outcome measures that will be taken throughout the study. By choosing models that utilize longitudinal data, we will further increase the power to detect differences between arms

2. Data Analytic Plan

Statistical analyses will be performed using SAS 9.4. P-values less than .05 will be considered statistically significant. Baseline demographics and smoker characteristics will be summarized by groups (JUUL and NRT), as appropriate. Continuous variables will be presented as mean \pm SD and compared among the 2 groups using ANOVA test. Categorical variables will be presented as counts and proportions and compared among the 2 groups using the chi-squared test.

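### The missing-data weights are defined as the inverse of the probability of being missing, when they should be the inverse of the probability of being observed

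*Combined protocol and SAP*

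**What the plan says.** Section E.3 sets out two approaches to missing data. The first is introduced with "First, we will use inverse probability weighting with propensity scores" and described in two steps. In step one, "we first model the probability of missingness as a function of baseline covariates and previous outcomes". In step two, "the inverse of the resulting predicted probabilities (from the logistic regression model) will serve as weights in our proposed model of the response". The second approach is a comparison: "We will compare these results to a more conservative ITT approach as a final step". The rule that this comparison would apply to missing outcomes is not given.

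No sentence in the document describes the modelled probability as that of being observed or retained, takes its complement, or mentions stabilised or truncated weights.

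Section E.1 (Power Analysis) supplies the planning figures used below: 20% attrition, and complete substitution of 35% with JUUL and 20% with NRT.

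**The concern.** Weighting for dropout works by letting retained participants stand in for similar people who left, so those who most resemble the dropouts must count most. The weight that does this is 1/P(observed). The predictions from step one are probabilities of being missing, and step two inverts those same predictions. Participants who most resemble the dropouts therefore count least.

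This is the first of only two safeguards against missing data. It matters most for complete substitution, the primary outcome, which Section E.2 analyses under Hypothesis 1a by logistic regression and GEE; the likelihood argument in E.2 is made for the mixed models of Hypothesis 1b. The missingness model includes earlier outcomes. If these predict both dropout and later substitution, which is the case weighting is meant to handle, the reversed weights add bias. Code written this way would run without an error message.

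**Working it through.** **Plan's own figure.** The plan gives no number for the weights. The nearest stated figure is power above 80% with 300 analysed. With 150 per arm, 35% vs 20% and two-sided 0.05:

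z = [0.15·√150 − 1.96·√(2 × 0.275 × 0.725)] / √(0.35 × 0.65 + 0.20 × 0.80) = (1.837 − 1.238)/0.622 = 0.963, so power is 83.2%. Exact Fisher power is 80.3%.

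The stated power reproduces. The point about the weights does not depend on it.

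**Weights for a retained participant**

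| P(missing) | As written, 1/p | Correct, 1/(1 − p) |
|---|---|---|
| 0.05 | 20.0 | 1.05 |
| 0.10 | 10.0 | 1.11 |
| 0.20 | 5.0 | 1.25 |
| 0.30 | 3.33 | 1.43 |
| 0.40 | 2.5 | 1.67 |

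The written weight falls as dropout risk rises; the correct weight rises.

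**Two-group illustration.** From the plan: 20% attrition and average substitution of 35% and 20%. Assumed: two equal groups, L with 10% dropout and H with 30%, the same in both arms.

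The share of group L in each estimate is:
- truth, and correct weights: 0.500
- no weights: 0.9/(0.9 + 0.7) = 0.5625
- as written: (0.9/0.1)/(0.9/0.1 + 0.7/0.3) = 9/11.33 = 0.794

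Bias in an arm's rate is (share − 0.5) × (rate in L − rate in H). The ratio of written to unweighted bias is 0.294/0.0625 = 4.7, whatever the rates.

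| Assumed rates, L/H | Method | JUUL | NRT | Difference (points) |
|---|---|---|---|---|
| JUUL 45/25, NRT 28/12 | Correct | 35.0 | 20.0 | 15.0 |
| | Unweighted | 36.3 | 21.0 | 15.3 |
| | As written | 40.9 | 24.7 | 16.2 |
| JUUL 60/10, NRT 36/4 | Correct | 35.0 | 20.0 | 15.0 |
| | Unweighted | 38.1 | 22.0 | 16.1 |
| | As written | 49.7 | 29.4 | 20.3 |

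For example, JUUL in the first scenario as written is (9 × 45 + 2.33 × 25)/11.33 = 40.9.

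**Effective sample size**, (Σw)²/Σw², as a fraction of those randomised:
- as written: [0.5(9 + 2.33)]² / [0.5(0.9 × 100 + 0.7 × 11.11)] = 32.11/48.89 = 0.66
- correct: 1/[0.5(1/0.9 + 1/0.7)] = 0.79

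**Second set of assumptions.** Final substitution is 70% in earlier switchers and 10% in earlier non-switchers, with 20% missing in each arm. The ratio of missingness, non-switchers to switchers, is varied.

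| Ratio | As written, JUUL vs NRT (difference) | Unweighted (difference) |
|---|---|---|
| 1 | 35.0 vs 20.0 (15.0) | 35.0 vs 20.0 (15.0) |
| 1.5 | 42.5 vs 24.8 (17.7) | 36.4 vs 20.7 (15.7) |
| 2 | 47.5 vs 28.8 (18.7) | 37.3 vs 21.1 (16.2) |
| 3 | 53.7 vs 35.0 (18.7) | 38.4 vs 21.6 (16.8) |

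Correct weights return 35.0 vs 20.0 throughout.

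**Different dropout patterns by arm.** Let only the NRT arm have the 10%/30% pattern, with the milder rates (28/12), and let JUUL dropout be unrelated to group. JUUL stays at 35.0. NRT is 24.7 as written and 21.0 unweighted. The odds ratio is (0.35/0.65)/(0.247/0.753) = 1.64 as written and 2.03 unweighted, against a true 2.15. The difference is 10.3 points as written, against a true 15.0.

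**The case against.** The strongest reply is that this is loose wording. The method is named, and in that method the weight is the inverse of the probability of the status a participant actually had. Only people with an outcome enter the response model, so the intended probability would be that of being observed. That may be what the authors meant. The text nevertheless says which probability is modelled and that its predictions are inverted, and nothing else in the document points the other way.

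Second, the harm is conditional. If missingness is unrelated to predictors of outcome, there is no bias, and the group-specific rates above are assumptions. This stands.

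Third, the contrast between arms is distorted less than the rates. In the milder two-group scenario the difference is off by 1.2 points. On the odds-ratio scale that logistic regression uses (truth 2.15), the written weights give 2.11 and 2.37 in the two-group scenarios, and 2.24, 2.24 and 2.15 at missingness ratios 1.5, 2 and 3. Unweighted values are 2.14, 2.19, 2.19, 2.23 and 2.26. At ratio 3, and on this scale, the written weights come closer to the truth than no weighting. The near-cancellation needs the same dropout pattern in both arms, however. With the pattern in one arm only, the odds ratio falls to 1.64. Two arms given different products have no guarantee of matching dropout.

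Fourth, the reach is limited. The Fisher test in E.1 is described without weights, and the likelihood-based mixed models do not need them. This also stands. The comparison with an ITT approach is a weak safeguard, because its rule is undefined and a disagreement would not show which analysis was wrong.

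**Conclusion.** The concern holds. As written, E.3 specifies 1/P(missing), which is not a valid weight for retained participants and reverses the intended correction. Whenever dropout is related to outcome in the scenarios examined, the estimated arm rates lie further from the truth than with no weighting. With 10% and 30% dropout in two equal groups the bias in each rate is about 4.7 times as large, and the effective sample falls to 66% of those randomised, against 79% with correct weights. The effect on the treatment contrast ranges from negligible to material: a true 15-point difference becomes 16.2 or 20.3 points when both arms share the dropout pattern, and 10.3 points when only the NRT arm has it.

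Only the 20% attrition and the 35% and 20% rates come from the plan; the risk groups and their outcomes are assumed. The error is confined to the weighted analysis, but it is an error in the stated rule and must be corrected before analysis.

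**What to change.** Replace the two sentences that describe the steps with wording such as:

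> We will fit a logistic model for the probability that the outcome is observed, given baseline covariates and earlier outcomes. Each participant with an observed outcome will be weighted by the inverse of that probability, stabilised by the marginal probability of being observed. Standard errors will be robust.

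The first part, modelling the probability of being observed and inverting it, is the correction. Stabilisation and robust standard errors are good practice to state at the same time, along with the covariate list, how weights are formed at each visit, and any truncation rule.

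The cost is a sentence or two of SAP wording. No data collection, sample size or operational procedure changes.

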Switching to a Vaping Device: Evaluating Risk Reduction among Quitline Treatment Failures

Aim 1: The focus of aim 1 is the examination of differential levels of (Hyp 1a) substitution between JUUL and NRT, and (Hyp 1b) reported nicotine craving, withdrawal symptoms, number of cigarettes smoked per day, product abuse liability, and nicotine dependence, between JUUL and NRT. *Hypothesis 1a:* Complete substitution rates, at the 8 and 12 week follow-ups, will be compared between JUUL and NRT arms using logistic regression analysis, adjusting for baseline variables such as age, gender, number of cigarettes per day and/or randomization stratification factors. The GEE model will be performed for the repeated measure analysis of complete substitution rate across multiple visits. *Hypothesis 1b:* If needed, we will apply a normalizing transformation to the response measure (e.g., taking the logarithm of cigarettes per day) before proceeding with the analysis, as a means of removing the effects of potential outliers. We will examine changes in each outcome over time across the two groups using linear mixed model (LMM) regression analysis. We will employ a random intercept or slope parameter, as appropriate, and model the covariance structure for the repeated outcome measures, while accounting for baseline value of the outcome and potential confounders (including any variables not equally distributed between groups). Modeling is done using a likelihood-based approach and thus makes use of all available data (on the intention-to-treat (ITT) sample) to produce consistent estimates of the regression parameters. Contrast estimates comparing group effects over time will be used as measure of effect. A similar approach will be used to explore the EMA data collected.

Aim 2: The focus of aim 2 is the examination of changes in a biomarker of toxicant exposure. *Hypothesis 2:* We will examine changes in iCO, a biomarker of toxicant exposure, and EMA data using the methods outlined in Hypothesis.

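### The week-8 Fisher's exact test, as written, is an unweighted completers analysis: IPW cannot enter it, ITT is undefined, and no rule covers missing substitution status

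*Combined protocol and SAP*

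**What the plan says.** Section E.1 (Power Analysis) states: "Complete substitution of combustible cigarettes for EC products is the primary outcome of the study". The arms are compared "at the end of the product trial phase (8-week follow-up) using the Fisher's exact test". The planned rates are 35% (JUUL) and 20% (NRT), with 20% attrition overall and no split by arm. The enrolled sample "will allow 300 participants to be analyzed in the final sample", and power above 80% is claimed "for a two-sided .05 level chi-squared test".

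Section E.2 (Data Analytic Plan) gives Hypothesis 1a a different method: substitution rates at weeks 8 and 12 "will be compared between JUUL and NRT arms using logistic regression analysis", with baseline adjustment, plus a GEE model across visits. It states no analysis set for these models. An ITT sample is mentioned only for the Hypothesis 1b mixed models.

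Section E.3 (Missing Data) says of participants who refuse or lose contact: "we will censor data at point of loss". Two approaches follow. The first is IPW, with missingness modelled on baseline covariates and previous outcomes and the weights placed in the response model. The second is the closing comparison: "We will compare these results to a more conservative ITT approach as a final step". The section does not say what that approach does with an unknown week-8 status.

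**The concern.** The endpoint is a yes/no status at one time point. Censoring has no meaning for it, so a participant lost before week 8 simply leaves the Fisher table. The only analysis that appears meant to keep everyone randomised comes last and is undefined.

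Informative loss is plausible. Section D.3 (Measures) requires seven days of diary data with daily CO readings at or below 6 ppm, and section D.1 lists the twice-daily assessment burden as a weakness. The arms receive visibly different products, and E.1 itself notes that participants have already tried NRT without success. People who return to smoking may stop sending data, and may do so more in one arm. A completers comparison could then show a difference in either direction where none exists, or misstate the size of a real one. With the test, the analysis set and the missing-data rule all open, the choice could also be made after the data are seen.

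**Working it through.** **Inputs.** From E.1: 35% and 20%, 20% attrition, 420 randomised (210 per arm if split equally), 300 analysed, two-sided 0.05. Assumed here, because the documents do not give them: the split of losses by arm and the link between loss and outcome.

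**Formula.** For the pooled two-proportion (chi-squared) test with d = p1 − p2, s0 the pooled standard error and s1 the unpooled one, the rejection probability is Φ((d − 1.96·s0)/s1) + Φ((−d − 1.96·s0)/s1).

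**1. The plan's own figure.** At 150 per arm, 0.35 vs 0.20: s0 = 0.0516, s1 = 0.0508, power = Φ((0.15 − 0.1011)/0.0508) = 0.832. The claim of more than 80% reproduces; exact enumeration for Fisher's test gives 0.803. The counts do not reconcile: 420 × 0.8 = 336, 186 × 2 × 0.8 = 297.6, and 300 of 420 would be 28.6% loss.

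**2. What happens to a participant lost before week 8.**

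| Analysis | Section | Treatment of the lost participant |
|---|---|---|
| Fisher's exact test | E.1 | Excluded; the test takes no weights |
| Logistic / GEE | E.2, E.3 | Not used directly; weights can correct for loss explained by baseline covariates and previous outcomes |
| ITT comparison | E.3 | Not defined |

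**3. Type I error of the completers test.** True rate 20% in both arms, 210 per arm, every dropout a failure. The completer rate is 0.20/(1 − loss).

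| Loss by arm | Completer rates (n) | d | s0, s1 | Type I error |
|---|---|---|---|---|
| 20% / 20% | 0.250 (168) vs 0.250 (168) | 0 | 0.0472, 0.0472 | 5.0% |
| 15% / 25% | 0.235 (178.5) vs 0.267 (157.5) | −0.031 | 0.0473, 0.0474 | 10.2% |
| 10% / 30% | 0.222 (189) vs 0.286 (147) | −0.063 | 0.0476, 0.0480 | 26.8% |

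Simulation agrees. At 186 per arm the last two are about 9.7% and 24.4%. Simulating Fisher's test itself at 210 per arm gives about 8.7% and 25%. The arm that loses more failures looks better, so reversing the split reverses the sign.

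**4. Estimate under the planned effect, equal 20% loss, all failures.** 0.35/0.8 − 0.20/0.8 = 0.4375 − 0.25 = 18.75 points (18.7 in simulation), against a true 15.

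**5. Counting missing as not substituted, 210 per arm.**
- Dropouts all failures: type I error stays at about 5% for every split in step 3.
- Dropout unrelated to outcome, 15% vs 25%: observed rates 0.20 × 0.85 = 0.17 and 0.20 × 0.75 = 0.15; s0 and s1 both about 0.0358; type I error 8.6%. The completers test is then valid, at about 5%.

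**6. Power cost at the same loss, if 35% and 20% are completer rates.**

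| Loss | Completers | All 420, missing = not substituted |
|---|---|---|
| 20% | 35% vs 20%, 168 per arm: 87.2% | 28% vs 16%, 210 per arm: 84.6% |
| 28.6% | 35% vs 20%, 150 per arm: 83.2% | 25% vs 14.3%, 210 per arm: 79.1% |

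If 35% and 20% are instead rates among all randomised, power at 210 per arm is 93.4%.

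**The case against.** Fisher's test is named only in the power section. E.2 assigns the hypothesis to adjusted logistic regression and GEE, and E.3 places its weights in a response model, which fits those. If the logistic model is primary, IPW does apply. In a simulation where dropout depended on arm and an observed predictor, weighting brought type I error from 7.1% to 4.8%. This stands, but the plan does not say which analysis is primary, and IPW does not help when loss follows an unrecorded relapse.

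The plan also does include an ITT comparison and calls it conservative. Section B contrasts responder quit rates with intent to treat, which suggests the authors mean ITT to retain non-responders, and the D.3 definition arguably cannot be met without diaries and CO readings. That supports reading ITT as missing = not substituted, but the text never says so and does not give it first place.

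A reader might infer that the plan fixes the primary analysis set at 300. It does not: 300 is a planning figure, inconsistent with 420 at 20% attrition.

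A reader might also infer that failure-related dropout by itself inflates type I error. It does not; the loss must also differ by arm. The documents give no arm-specific attrition, and 10% vs 30% is extreme beside the retention above 80% cited in section D.2.

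**Conclusion.** The point holds as a gap in specification with a conditional risk. The Fisher comparison, as written, excludes lost participants and cannot be weighted. ITT is undefined, and three methods are named for one hypothesis without a ranking. Type I error of about 10% to 27% arises only if dropout is both failure-related and unequal between arms, at the assumed splits; with equal loss it is 5%, and the harm is an overstated effect (about 18.7 points for a true 15).

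Two tempting conclusions about the remedy are not supported. It is not free of power cost: setting 84.6% for all 420 at 20% loss against 83.2% for 300 completers compares different loss rates. Nor is missing = not substituted always protective, since it has 8.6% type I error at 15% vs 25% loss unrelated to outcome. It suits this endpoint because success requires verification, but it needs the other analyses beside it.

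**What to change.** In E.1 to E.3:
- Name one primary week-8 analysis, either Fisher's exact test or the adjusted logistic model, and use the same name in each section.
- State that it includes all randomised participants in their assigned arm, with no verified week-8 status counted as not substituted, and define ITT in those words.
- Remove "we will censor data at point of loss" for this binary endpoint.
- Keep the IPW-weighted logistic model and the observed-data analysis as sensitivity analyses, ideally with one that varies informative dropout by arm. Report loss by arm.
- Reconcile 420, 186 per group and 300 with the 20% attrition.

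The cost is wording only. Absolute rates will be lower in both arms. If the planned rates are completer rates, power falls by about 3 to 4 points against completers at the same loss, and to just under 80% at 28.6% loss.
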